“Clinical trials of medicinal products involving a minor or a child may be conducted only if the relevant medicinal product is intended for the treatment of paediatric diseases or if the purpose of the clinical trial is to optimise the dosing or regimen of the medicinal product accordingly for children or minors” and on other aforementioned data, a paediatric population **may** be included in this clinical study without prior full completion of clinical trials involving competent adult subjects.

As part of this clinical study, all patients will receive the investigational medicinal product BP-SCIG 20%, solution for subcutaneous administration, manufactured by BIOPHARMA PLASMA LLC subcutaneously.

The IMP BP-SCIG 20% will be administered at the frequency of once a week for 52 weeks, subcutaneously using a CRONO S-PID4 infusion pump, at the dose of 0.1–0.2 g/kg once a week (the dose over 4 weeks is 0.4–0.8 g/kg).

The dosing regimen shall be designed to achieve a minimum IgG level (at least 5–6 g/L), which will be measured monthly before each IMP infusion.

Efforts must be taken to maintain serum IgG within the reference range for the corresponding age group of patients.

Individual dose selection and adjustment may be required for each patient, depending on the pharmacokinetic response (IgG level) and clinical response. Threshold levels must be assessed in combination with the incidence of infectious episodes.

Dose adjustment of the IMP BP-SCIG 20% based on threshold IgG levels is performed by the Investigator based on the clinical presentation of each individual patient.

A loading dose of IMP may be required (at the Investigator’s decision): at least 0.2–0.5 g/kg (1.0–2.5 mL/kg) of body weight per week. This dose is distributed across several days, with a maximum daily dose of 0.1 to 0.15 g/kg.

After achieving a steady-state (minimal) level of IgG, maintenance doses are administered at repeated intervals (approximately once a week) to achieve a cumulative monthly dose of 0.4–0.8 g/kg. Each single dose must be administered to different anatomical locations.

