 - Paediatric patients are required to undergo Visits 1 and 2 of the screening period. In the event of meeting the criterion “total serum IgG level ≥ 5 g/L – as confirmed by the results of at least two (2) measurements performed immediately prior to the subsequent administration of IVIG after signing the ICF”, the patient proceeds to treatment with the IMP BP-SCIG 20%, starting from Cycle 1. If the criterion is not met, then Visit 3 is performed.

- Adult patients are required to undergo Visits 1 and 2 of the screening period to determine whether they meet inclusion/non-inclusion criteria, and Visit 3 of the screening period to conduct a mandatory pharmacokinetic assessment of BIOVEN.
- For Cohort C, newly diagnosed (treatment-naïve) patients are required to undergo Visit 1 of the screening period; if meeting inclusion/non-inclusion criteria, the patient proceeds to treatment with the IMP BP-SCIG 20%, starting from Cycle 1.

Study phases. Treatment period.

The phase begins after the end of the screening period.

Cycles 1–13: These include on-site visits to the CTS: 4 visits in Cycle 1; all subsequent cycles: each first visit of the cycle (every 28 days \pm 3 days) and interim self-administrations of the product by patients in the home (every 7 days \pm 1 day) for 52 weeks. A total of 13 cycles that include 13 main on-site visits (1 visit to the CTS in each cycle), and 3 on-site visits for interim administration of the IMP. The period lasts 52 weeks.

Individualised dose titration is performed.

A loading dose of IMP may be required (at the Investigator's decision): at least 0.2–0.5 g/kg (1.0–2.5 mL/kg) of body weight. This dose is distributed across several days, with a maximum daily dose of 0.1 to 0.15 g/kg.

After achieving a steady-state level of IgG, maintenance doses are administered at repeated intervals (approximately once a week) to achieve a cumulative monthly dose of 0.4–0.8 g/kg. Each single dose must be administered to different anatomical locations. (see Section 6.1 of this Protocol).

Pharmacokinetic parameters of the IMP are assessed at Week 21 (see Table 4.2.2)

Cycle 1:

- Visit 4 (C1W1): **On-site visit** Week 1 – the first administration of the IMP BP-SCIG 20%;
- Interim administration 1(C1W2) on-site – Week 2, administration of the IMP;
- Interim administration 2(C1W3) on-site – Week 3, administration of the IMP;
- Interim administration 3(C1W4) on-site – Week 4, administration of the IMP.

Cycle 2:

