5.3 Subject exclusion criteria (discontinuation of treatment with the investigational product)

Table 5.3.1 – Exclusion criteria for CT subjects

No.	Exclusion criterion
1.	at the request of the patient/patient's parents/patient's legally authorised representative at any time and for any reason;
2.	patient developing serious and/or unexpected AEs/ARs during the study, which require discontinuation of the product;
3.	blood transfusions or transfusions of blood components and products, with the exception of the IMP;
4.	the need to use medicinal products disallowed as part of this study;
5.	systematic lack of patient compliance with the treatment regimen prescribed by the Investigator;
6.	systematic lack of patient compliance with the procedures specified in this protocol;
7.	exclusion based on screening results, including emergence of episodes of serious bacterial infections while receiving a previous IV immunoglobulin product and episodes of hospitalisation during the screening period (before the first administration of the IMP BP-SCIG 20%).

For all subjects withdrawn from the study due to AEs requiring discontinuation of treatment with the investigational medicinal product, it is required to conduct the final visit procedures as soon as possible after AE development. After discontinuation of treatment, the subject shall remain under observation until the reaction or its clinically significant signs disappear.

The reasons for leaving the study early must be documented in the eCRF.

Table 5.3.2. Criteria for exclusion of CT subjects from the investigation of PK parameters at the time of starting PK assessment

No.	Exclusion criterion
1.	Receiving the IMP BP-SCIG 20% for less than 4 months;
2.	Presence of episodes of serious bacterial infections (bacteraemia or sepsis, bacterial meningitis, osteomyelitis/septic arthritis, bacterial pneumonia, visceral abscess) at the time of investigation of PK parameters.

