6. TREATMENT OF SUBJECTS

6.1. Treatment regimen

The IMP shall be administered subcutaneously.

All patients will receive the investigational medicinal product BP-SCIG 20%, solution for subcutaneous administration manufactured by BIOPHARMA PLASMA LLC.

The IMP BP-SCIG 20% shall be administered at the frequency of once a week for 52 weeks, subcutaneously using a CRONO S-PID4 infusion pump.

The dosing regimen shall be designed to achieve a trough IgG level (at least 5–6 g/L), which will be measured before the next infusion.

Efforts must be taken to maintain serum IgG within the reference range for the corresponding age group of patients.

Individual dose selection and adjustment may be required for each patient, depending on the pharmacokinetic response (IgG level) and clinical response. Threshold levels must be assessed in combination with the incidence of infectious episodes. To reduce the risk of infection, it may be necessary to increase the dose and aim to achieve higher trough IgG levels.

A loading dose of IMP may be required (at the Investigator's decision): at least 0.2–0.5 g/kg (1.0–2.5 mL/kg) of body weight. This dose is distributed across several days, with a maximum daily dose of 0.1 to 0.15 g/kg.

After achieving a steady-state (minimal) level of IgG, maintenance doses are administered at repeated intervals (approximately once a week) to achieve a cumulative monthly dose of 0.4–0.8 g/kg. Each single dose must be administered to different anatomical locations.

Since the bioavailability of SCIGs is 30 % lower than that of IVIGs, partly due to binding to the extracellular matrix and cleavage by tissue enzymes (Wang et al. 2008; Berger et al. 2013), a dose adjustment factor of 1.37 will be used to convert the IVIG dose to the SCIG dose. This is based on historical data for bioequivalence evaluation of these administration routes (Wasserman et al. 2010, 2011; Berger et al. 2011) and meets the requirements of the US Food and Drug Administration (US FDA), according to which the SCIG doses must be adjusted to ensure an equivalent AUC for total IgG compared to previous IVIG therapy. Dose calculation for patients who received IVIG prior to the start of their participation in the study (John W Sleasman et al. 2019):

The initial dose of SCIG

$$\text{IgG} = \frac{\text{Previous IVIG dose (in grams)} \times 1.37}{\text{Number of weeks between IVIG administrations}}$$

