The dose adjustment factor of 1.37 will be evaluated in an interim pharmacokinetic (PK) analysis and modified as needed.

The first four IMP administrations are for training purposes, during which the investigational medicinal product BP-SCIG 20% for subcutaneous administration will be administered by a responsible member of the study team in a hospital setting and by the patient/legally authorised representative or parents after an appropriate training and in compliance with aseptic/antiseptic precautions under the supervision of responsible and trained members of the study team.

The study doctor prescribes the dose and rate of subcutaneous administration of the IMP for home-based use. The patient/their legally authorised representative or parents will be instructed by the Investigator regarding the use of the CRONO S-PID4 infusion pump, the administration technique, filling out the patient's diary, recognition of adverse reactions and measures to be taken in the event of adverse reactions.

Prior to use, the solution must be at room temperature and remain outside the refrigerator for at least 30 minutes. Turbid solutions and/or solutions with sediment must not be used.

To administer the IMP, a CRONO S-PID4 infusion pump and a dedicated single-use infusion set are used.

The IMP BP-SCIG 20% can be administered in sites with ample subcutaneous fat, such as the abdomen, the shoulder, and lateral thigh.

The IMP BP-SCIG 20% is administered subcutaneously using a CRONO S-PID4 infusion pump. Multiple lines can be used for administration into several sites simultaneously. It is recommended to use an initial infusion rate of 10 mL/h/line. If well tolerated, the infusion rate may be increased by 5 mL/h/line at each subsequent administration. The recommended maximum rate is 25 mL/h/line. The amount of product infused into a certain site must not exceed 25 mL. In infants and children, the administration site can be rotated every 5–15 mL. For adults, doses above 30 mL can be divided into several doses, in accordance with the patient's preferences. There are no limitations regarding the number of injection sites.

Hypersensitivity to active ingredient or any of the excipients is a contraindication.

The product must not be administered via the intravascular route. If BP-SCIG 20% is inadvertently administered into a blood vessel, the patient may develop shock. In the event of shock, standard treatment of shock must be instituted.

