9.6 Assessment of pharmacokinetic data

Analysis of pharmacokinetic parameters.

The main pharmacokinetic parameters include:

1. AUC-t value. Steady-state area under the concentration-time curve (AUC) for the total IgG level shall be compared with the values for the prior therapy (BIOVEN) for the relevant patient cohorts.
2. Trough IgG levels. The monthly trough IgG levels obtained, measured after 4 months of treatment with the IMP, prior to the next infusion, once every 4 weeks, over 6 months, shall be compared with the trough levels for at least two prior infusions of the previous SCIG or IVIG product. For treatment-naïve patients, a descriptive comparison with the data in published literature (if available) is required.

Methods of descriptive statistics: n, arithmetic mean, standard deviation, the median and the percentiles, the minimum and maximum values (depending on the type of distribution), including the plotting of graphs and charts and methods of interval estimation.

To evaluate the significance of changes over time in the event of assessing the parameter at two visits (before and after) in the case of quantitative variables, the analysis will use Student's t-test for paired data or Wilcoxon signed rank test – depending on the results of checking the normality of the distribution of difference [after - before] using the Shapiro-Wilk test. In order to assess changes over time in the event of measuring variables at more than two visits, methods of one-way analysis of variance (ANOVA) with subsequent application of post hoc analysis using Tukey's test will be used. In order to compare by those variables, by which the data were heterogeneous at baseline, covariance analysis (ANCOVA) will be used. In order to check the preconditions for the use of analyses of variance and covariance, the normality of distribution of the data and their residuals will be tested using the Shapiro-Wilk test. If the residuals are not distributed normally, or if the data do not pass the normality check, a corresponding rank analysis will be performed.

For the Shapiro-Wilk test, the significance level will be set at 0.01, and for other tests it will be set at 0.05. If a multiple comparisons effect occurs, significance level adjustments will be applied using the Holm method or Benjamini-Hochberg method.

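### Steady state for the Week 21 PK profile and the monthly troughs is counted from the first infusion, not from the last dose change, so recently adjusted patients can enter the comparison with BIOVEN as steady-state

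*Protocol*

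**What the plan says.** **The clock.** Section 4.1 equates steady state with four months of treatment for the primary pharmacokinetic endpoint, the mean trough over the following six months. Sections 4.2 and 6.3.9 place the BP-SCIG 20% profile at Week 21, in at least 20 adults who have had the product for at least four months without severe bacterial complications. Table 5.3.2 excludes a subject from the profile on two grounds only: "Receiving the IMP BP-SCIG 20% for less than 4 months", or a serious bacterial infection at the time.

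**The dose.** Section 2.4 says "Individual dose selection and adjustment may be required for each patient, depending on the pharmacokinetic response (IgG level) and clinical response", and adds that "Dose adjustment of the IMP BP-SCIG 20% based on threshold IgG levels is performed by the Investigator". Section 4.2 says of the treatment period, Cycles 1–13, that "Individualised dose titration is performed". Section 6.1 adds that, to lower infection risk, "it may be necessary to increase the dose and aim to achieve higher trough IgG levels". It also says of the conversion factor: "The dose adjustment factor of 1.37 will be evaluated in an interim pharmacokinetic (PK) analysis and modified as needed". None of these passages sets an end to adjustment before Week 21, and none restarts the four-month clock after a change.

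**The use.** Section 9.6 compares "Steady-state area under the concentration-time curve (AUC) for the total IgG level" with the BIOVEN values. Section 3 makes non-inferior AUC, and the factor that secures it, a primary objective; Section 4.1 lists both among the secondary pharmacokinetic endpoints.

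**The concern.** Time since the first infusion marks steady state only if the dose has stayed the same. IgG is eliminated slowly, so a dose change opens a new approach to a new plateau. Trough IgG is measured at every four-weekly cycle visit, so a Week 9 or Week 13 result can lead to a change at Week 13 or Week 17. The Week 21 profile then falls eight or four weeks after that change, and the patient still meets every entry condition.

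After an increase, the AUC is too low for the dose being given and apparent clearance (dose over AUC) is too high. After a reduction, both errors reverse. The AUC feeds a primary objective and the recalculation of the dose factor. Adults who start on the converted dose and then need adjusting are informative about that factor, and theirs are the profiles at risk. Entry and sampling time are protocol matters: a profile taken too early cannot be corrected later by analysis alone.

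**Working it through.** **Inputs from the protocol.** Profile at Week 21 over 7 days (Table 4.2.2); entry after four months (Section 4.2); factor 1.37 (Section 6.1); adult cohorts of 8–10 (Section 9.2).

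**Assumptions.** The protocol gives no IgG half-life and no typical dose change. I take half-lives h of 21, 30 and 40 days, first-order kinetics, all measured IgG from the product, and a dose change c of +25% for illustration.

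**Step 1: the protocol's own timing.** The Week 21 infusion falls 20 weeks = 140 days after the first, or 140/30.44 = 4.6 months. Four months is 17.4 weeks, so the entry rule is met. On a constant dose the fraction of steady state reached is 1 − 2^(−140/h) = 99%, 96% and 91%. For patients switching from earlier replacement, this fraction applies only to the difference between the old and new levels. Week 21 is adequate when the dose has not changed.

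**Step 2: clock from the last change.** For a profile starting d days after the change, with k = ln 2/h, the average fraction of the shift reached over the 7 days is

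f = 1 − [exp(−kd) − exp(−k(d+7))]/(7k),

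and the AUC relative to steady state on the current dose is (1 + c·f)/(1 + c).

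Example, d = 28: f = 0.65, 0.52 and 0.42. For c = 0.25 the ratios are 0.929, 0.903 and 0.884.

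| Change before profile (+25%) | h = 21 | h = 30 | h = 40 | AUC too low by |
|---|---|---|---|---|
| 1 week | 0.858 | 0.843 | 0.833 | 14–17% |
| 4 weeks | 0.929 | 0.903 | 0.884 | 7–12% |
| 8 weeks | 0.972 | 0.949 | 0.929 | 3–7% |
| 12 weeks | 0.989 | 0.973 | 0.956 | 1–4% |
| 16 weeks | 0.996 | 0.986 | 0.973 | 0.4–3% |

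A 20% reduction four weeks before gives 1.089, 1.121 and 1.145, so 9–15% too high. The planned range is "at the dose of 0.1–0.2 g/kg once a week"; a doubling across it four weeks before, which is an extreme case, gives (1 + f)/2 = 0.83 to 0.71, so 17–29% too low.

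**Step 3: consequences for one patient** (+25%, four weeks before). Apparent clearance is too high by 1/0.929 to 1/0.884, that is 8–13%. A factor recalculated from the current dose would move from 1.37 to 1.37/0.929 = 1.47 up to 1.37/0.884 = 1.55 through this artefact alone.

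**Step 4: consequences for a cohort.** If two of ten patients were affected in this way and contributed equally, the mean AUC would fall by 0.2 × 7–12% = 1.4–2.4%, about 2%.

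**The case against.** The strongest reply is that the problem may seldom arise where it matters. Adults compared with BIOVEN enter on at least four months of IVIG with two troughs of 5 g/L or more, and start on a converted dose. Sections 2.4, 4.2 and 6.1 describe maintenance dosing once a steady IgG level has been reached. Weeks 18–20 are home infusions with product issued at Week 17, so the one-week row of the table is unlikely. If part of the measured IgG is endogenous, the errors shrink: with a quarter to a third endogenous (an assumption), 7–12% becomes about 5–9%. Increases bias the AUC downward, which is conservative for non-inferiority, and reductions partly offset them.

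Most of this stands as a limit on size. It does not remove the point. The maintenance sentence neither bars later changes nor governs entry to the profile. A low AUC may be conservative for non-inferiority, but it inflates a recalculated factor.

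A reader might infer that non-steady-state AUCs are compared as a rule, that the protocol expressly permits adjustment at any time, or that the measured AUC bears no relation to the current dose. The documents support none of these. Only recently adjusted patients are affected; the freedom to adjust follows from the absence of a limit and is not stated; and four weeks after a 25% increase the AUC is still 88–93% of its plateau. Nor does the protocol support a rigid 12-week gate, which could cost profiles against the minimum of 20 adults.

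**Conclusion.** The point holds as a fault in the eligibility clock. Following the rules as written can label a recently adjusted patient's AUC as steady-state and carry it into the BIOVEN comparison. The same clock governs the monthly troughs.

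It concerns only patients whose dose changed in roughly the 8–12 weeks before Week 21, or shortly before a trough. Under the stated assumptions the individual AUC error for a 25% increase is about 7–12% at four weeks and 3–7% at eight. The number of such patients is unknown. If they are few, the cohort shift is small, but with 8–10 adults per cohort a few could matter. The change is worth making because it is cheap and because a mistimed profile cannot be retaken.

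**What to change.** - Record the date and size of the last BP-SCIG 20% dose change before the profile and before each trough. Section 4.9 already brings diary doses into the eCRF.
- In Sections 4.2 and 6.3.9 and Table 5.3.2, define the steady-state PK set by time on an unchanged g/kg dose. Justify the interval against the protocol's own four-month definition. As a guide, a 12-week minimum leaves at most about 4% error after a 25% increase, and 16 weeks at most about 3%.
- Where feasible, take a recently adjusted patient's profile at a later existing four-weekly on-site visit. Otherwise keep the Week 21 profile.
- In Section 9.6, base the steady-state AUC and dose-factor comparison on stable-dose profiles. Show profiles and troughs taken soon after a change separately or in a sensitivity analysis.

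The cost is protocol wording and some flexibility in the PK visit. Some profiles will come later, or fewer will enter the main comparison. The investigator's discretion over dosing is not touched.

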In accordance with the EMA guidelines “*Guideline on core SmPC for human normal immunoglobulin for subcutaneous and intramuscular administration*” EMA/CHMP/BPWP/143744/2011 rev.1 26 February 2015, and “*Guideline on the clinical investigation of human normal immunoglobulin for subcutaneous and/or intramuscular administration (SCIG/IMIg)*” EMA/CHMP/BPWP/410415/2011 rev.1 23 July 2015: the investigational medicinal product BP-SCIG 20% (Human normal immunoglobulin for subcutaneous administration) is used **for replacement therapy in primary immunodeficiencies with impaired antibody production** in adults and children (0–18 years).

At present time, the list of indications for SCIG products and age-defined framework are defined in accordance with the “*Guideline on core SmPC for human normal immunoglobulin for subcutaneous and intramuscular administration*” EMA/CHMP/BPWP/143744/2011 rev.1 26 February 2015.

Primary immunodeficiencies (PIDs) are congenital diseases of the immune system [26]. This is a group of heterogeneous rare diseases where the functioning of the immune system is impaired or individual links are not working. The International Union of Immunological Societies (IUIS) lists ten groups and 416 monogenetic primary immunodeficiencies (PIDs)/inborn errors of immunity. Predominant antibody deficiency represents the largest group; moreover, antibody deficiency is clinically relevant in many other PIDs [33].

Primary antibody deficiencies (PADs) are the most common types of primary immunodeficiencies, accounting for approximately 50–60 % of congenital immune system disorders. PADs comprise a heterogeneous group of immune defects characterised by insufficient antibody production in response to antigens. The PAD spectrum is diverse, ranging from selective IgA and IgG subclass deficiencies to severe agammaglobulinaemia with complete absence of B lymphocytes [34]. Congenital antibody production deficiencies have a similar clinical phenotype characterised by increased susceptibility to bacterial infections, while autoimmune diseases and malignant neoplasms are also characteristic of certain forms of antibody production deficiencies [35]. The importance of antibodies is clearly demonstrable by the high infection-associated morbidity and mortality in patients with primary immunodeficiency diseases (PIDs), which are typically associated with impaired antibody production. The onset of PAD can occur at a different age, depending on the immune defect. Early diagnosis and timely initiated adequate treatment are key factors in prolonging the life of patients with congenital antibody production deficiencies and improving its quality. Late diagnosis and/or inadequate treatment lead to irreversible organ and system damage due to severe recurrent infections, resulting in early death of the patients. Most patients with antibody production deficiencies can live normal lives while receiving regular replacement therapy with immunoglobulin products.

Antibodies are required for protection against infections not only because they specifically recognise a plethora of microorganisms, but also due to their effector capacity, which includes neutralisation, opsonisation, antibody-dependent cytotoxicity, and clearance of immune complexes.

Common variable immunodeficiency (CVID) is the most frequent form of significant antibody deficiency, affecting both children and adults. This is a genetically heterogeneous group of immune system defects characterised by hypogammaglobulinaemia with a deficiency of at least two immunoglobulin classes (predominantly IgG and IgA and/or IgM) in a setting of normal or

reduced counts of B lymphocytes, an increased risk of developing infectious diseases, and, in some patients, the development of autoimmune and granulomatous complications. The overall prevalence of CVID is estimated to range between 1:25,000 and 1:50,000 [36].

Among the most severe PIDs manifesting early in life are severe combined immunodeficiencies (SCIDs), which are characterised by pronounced T- and/or B-lymphopenia. Patients with SCID are usually born without clinical signs of the disease, but the disorder manifests within the first year of life, most often during the first months, with severe infections. Without timely diagnosis and adequate treatment, the children do not survive. The use of replacement immunotherapy allows not only preserving their life but also ensuring its quality.

The prevalence of PID

The incidence rates and prevalences of primary immunodeficiencies vary significantly across regions with different populations. Thus, in the USA, newborn screening for SCID has revealed a SCID incidence of 1:58,000, demonstrating a substantially higher incidence of SCID than previously estimated. Based on data from the USA, the prevalence of clinically significant immunodeficiency is estimated to be between 1:1,200 and 1:2,000. Epidemiological calculations based on this data suggest the presence of primary immunodeficiency in Europe in approximately 600,000 people. At the same time, in 2014, only 19,355 patients were registered in the patient registry of the European Society for Primary Immunodeficiencies (ESID registry).

As of 2021, the number of registered individuals with PIDs in Ukraine is 1,220, of whom 1,040 are alive. However, based on global estimates, this figure apparently does not reflect the true situation due to insufficient detection of such patients, which in turn leads to their disability and premature death. According to an American study, the average delay from the onset of the first symptoms to diagnosis was approximately 4.7 years; moreover, the higher the age at diagnosis, the greater the associated mortality. In contrast to that, early diagnosis enables timely implementation of appropriate therapeutic measures and improves patients' quality of life in health-related aspects.

Manifestation of PID

The majority of severe forms of antibody production deficiencies manifest in the first years of life; at the same time, common variable immunodeficiency and selective antibody production deficiencies may have clinical manifestations in any age. Some primary immunodeficiencies, including severe hypogammaglobulinaemia (especially in cases of severe combined immunodeficiency or agammaglobulinaemia), may manifest as an infection during the neonatal period or infancy, posing a threat to life. Early diagnosis and treatment initiation in patients with primary immunodeficiency helps prevent disability and premature death.

Early detection of PID in paediatric patients

Prenatal and neonatal screening for primary immunodeficiencies allows early diagnosis and prevention of severe infectious complications.

In recent years, numerous immunology experts at the international level have emphasised the need for the development and implementation of neonatal screening for SCID, allowing detection of affected individuals before the appearance of clinical symptoms. In Ukraine, SCID in children is detected immediately after birth owing to neonatal screening [37]. According to the Order of the Ministry of Health of Ukraine No. 2142 dated 01 October 2021, severe combined immunodeficiency (SCID) has been included in the list of diseases covered by the programme of expanded mass screening of newborns. Neonatal screening enables timely detection of combined primary immunodeficiencies, especially severe ones, allowing timely implementation of

preventive measures against infections, adequate treatment, and the preservation of children's lives and the improvement of their quality of life. Thus, owing to the implementation of modern diagnostic methods, including prenatal diagnostics and neonatal screening for SCID, it is possible to diagnose this condition in a timely manner and initiate replacement therapy from the first months of life.

Neonatal screening also detects X-linked agammaglobulinaemia, which accounts for over 85 % of agammaglobulinaemia cases and is caused by a mutation in Bruton's tyrosine kinase (Btk), which is essential for the normal maturation of B lymphocytes. Mutations in the Btk gene lead to a developmental arrest of B lymphocytes in the bone marrow, with almost complete absence of the cells in the peripheral blood of patients, down to 1 %. Serum immunoglobulin levels are extremely low, and there is no humoral response to antigens. Clinical symptoms appear in 50 % of patients with agammaglobulinaemia at 6–12 months of age, when maternal IgGs are catabolised, and almost all patients manifest by 5 years of age. In the presence of characteristic clinical and laboratory features, molecular diagnosis of immunodeficiency is recommended to verify the diagnosis. Upon identification of a Btk gene mutation, it is important to determine all mutation carriers within the family, which allows, as needed, prenatal diagnosis and the prevention of the birth of a child with severe immunodeficiency.

Abnormal susceptibility to infectious diseases is often the leading symptom of primary immunodeficiencies [25]. Chronic or recurrent infections of upper and lower respiratory tract, sinusitis and otitis media are the most common types of infections. Severe bacterial infections (SBIs) may also occur, such as sepsis, meningitis, septic arthritis, and osteomyelitis.

To prevent infections, patients with primary antibody deficiency and hypogammaglobulinaemia (reduced IgG), with absent or reduced production of specific IgG antibodies, as well as an abnormal susceptibility to infection, must receive long-term (often lifelong) immunoglobulin replacement therapy. The main principles of immunoglobulin replacement therapy are outlined in the Standard of Medical Care "Diagnosis and Treatment of Primary Immunodeficiencies".

Expected outcomes of effective Ig therapy include: absence of severe infections; achieving remission of chronic diseases and eradication of chronic infectious foci; serum IgG levels not lower than 4.5 g/L before the next administration of Ig products (the optimum is the IgG level of 6 g/L or higher); absence of exacerbations of autoimmune, allergic, or immunoproliferative diseases; preservation of working capacity and improvement in quality of life.

2.7 References to the literature and data related to the trial and forming the basis for its conduct.

